
- Individual PK parameters such as area under the plasma concentration-time curve (AUC) or maximum plasma concentration (C_{max}) will be derived using a population PK modelling approach, which is described in a separate data analysis plan (DAP).- Exploratory assessment of the relationship between individual PK parameters and PD endpoints for efficacy or safety may be performed; a separate DAP will be written.
Other measurements
Genomic Analysis
Genomic analysis for defining patient eligibility and stratification will be based on assessment of ctDNA in plasma with an oncogene panel. The genomic analysis includes a series of genes frequently mutated in cancer, but will be focused on the following genes: 
- BRAF CCI [REDACTED] CCI [REDACTED]- KRAS / NRAS CCI [REDACTED] CCI [REDACTED]- EGFR-ECD CCI [REDACTED]
Futuximab/modotuximab Immunogenicity
ADA in serum will be measured
Quality of life assessments (QoL)
QoL assessments will be performed at baseline, after the end of cycle 1 (C2D1), then from cycle 3 (C3D1) every 2 cycles during the treatment period, at the withdrawal visit, and every 8 weeks (2 months) during the follow-up period until death or until end of the study is reached (whichever occur first), using EORTC QLQ-C30 and EQ-5D-5L questionnaires Appendix 5 and Appendix 6 .
Data Monitoring Committee:
Safety data collected during the Safety Lead-In part will be reviewed by a Data Monitoring Committee (DMC) to assess whether 1) the drug combination is tolerable, 2) if the maximum tolerated dose (MTD) has been exceeded, and 3) if the randomised portion of the study may proceed.
During the Safety Lead-In part, the DMC will initially assess tolerability after 6 evaluable participants, then after 12 evaluable participants treated and finally when all 25 participants will have been treated.
During the Randomised part the DMC will meet approximately every 4 months in the first year and approximately twice a year thereafter and at the planned interim analysis as well. For more details see Section 4.1.3.4 .
The composition and role of the DMC will be described in a charter finalised before the trial is initiated.
Specific COVID-19 situation

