Follow-up period: After the withdrawal visit, all treated participants will be followed every 8 weeks (\pm 10 calendar days): 
 - For tumour assessment (unless patient had discontinued study treatments for radiologic disease progression or withdrawal of consent) until radiologic progression regardless of initiation of a new anticancer therapy - For survival status until death or until end of the study is reached (whichever occur first) If a participant is still receiving IMPs at the end of the study, please see Section 6.5 for procedures to be followed.
Criteria for evaluation: Efficacy measurements: Tumour assessments will be performed as per RECIST version 1.1 (Eisenhauer, 2009) at baseline and then every 8 weeks (\pm 7 calendar days) from C1D1 until radiologic progression, death or end of study, whichever occurs first.
Safety measurements: AEs will be graded using the National Cancer Institute Common Terminology Criteria for Adverse Events (NCI-CTCAE) version 5.0. AEs will be reported up to 30 calendar days after the last IMPs intake and the serious AEs

Name of the sponsor: I.R.I.S.
Name of Finished Product: Futuximab/modotuximab (also known as S95026 or Sym004)
Name of Active Ingredient: futuximab and modotuximab
related to the research product will be reported without any time delay. Information of any change or addition of a new concomitant treatment at each visit must be obtained. Safety assessments will include: 
- Concomitant medication/procedure surveys.- ECOG PS assessment.- Vital sign assessment (including temperature, pulse, respiratory rate, and blood pressure).- Physical examination (with weight, body surface area [BSA] calculation, and dermatologic examination).- Dermatologic examination (additional for futuximab/modotuximab participants in Safety Lead-In part and ARM A in Randomised part).- Haematology panel.- Biochemistry panel.- Serum magnesium (Mg), total calcium (Ca), potassium (K) monitoring (additional for futuximab/modotuximab participants in Safety Lead-In part and ARM A in Randomised part).- Coagulation panel.- Urinalysis.- Pregnancy testing (if applicable).- Electrocardiogram (ECG), 12-lead.

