Patients were randomly assigned in a 1:1:1 ratio to either of two dose regimens of futuximab/modotuximab, 12 mg/kg weekly (Arm A; 83 patients, 83 treated), loading dose of 9 mg/kg on Day 1 followed by maintenance dose of 6 mg/kg weekly beginning on Day 8 (Arm B; 86 patients, 84 treated), or to a control group treated with the investigator's choice (IC) therapy of capecitabine (61 patients), 5-FU (13 patients), or Best Supportive Care (BSC) (4 patients) (Arm C; 85 patients, 78 treated). The primary endpoint of the study was OS.

The primary endpoint was not met. Median OS in the intention-to-treat (ITT) population was 7.9 months (95% CI, 6.5-9.9), 10.3 months (95% CI, 9.0-12.9), and 9.6 months (95% CI, 8.3-12.2) for arms A, B and C, respectively (HR, 1.31; 95% CI, 0.92-1.87 for A vs C; and HR, 0.97; 95% CI, 0.68-1.4 for B vs C). Median PFS in the ITT population was 2.8 months (95% CI, 1.8-3.2), 2.7 months (95% CI, 2.6-3.3), and 2.6 months (95% CI, 1.4-3.1) for arms A, B, and C, respectively.

Response rates for evaluable patients in the ITT population were 11 PRs (14.1%), 8 PRs (9.6%), and 1 complete response (CR) and 1 PR (2.9%) in arms A, B and C, respectively. A per protocol analysis excluded patients from Russia as these patients were less refractory to standard EGFR mAb and considered more sensitive to therapy. For these reasons, this population was excluded from further analysis.

Baseline ctDNA mutation profiles of 70 genes (Guardant Health360 V2.9) were obtained from blood samples collected from 193 patients in the trial. An exploratory analysis of efficacy was carried out in a genetically defined subpopulation, which excluded patients with clonal RAS (KRAS/NRAS) and BRAF CCI (named double-negative [DN] mCRC; n = 170). This exploratory biomarker defined analysis showed an increase in median OS of 3.5 months in the DN mCRC population of patients treated with futuximab/modotuximab 9/6 (arm B; 11.9 months) compared with patients randomised to IC (Arm C; 8.4 months) (Figure (2.2.2) 1).

Figure (2.2.2) 1 - Kaplan-Meier curve of OS for the futuximab/modotuximab Sym004-05 patients with DN disease

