4.1.1. Study plan

This is a randomised, open label, multi-centre, two-arm Phase 3 study to evaluate futuximab/modotuximab in combination with trifluridine/tipiracil *versus* trifluridine/tipiracil monotherapy in participants ≥ 18 years of age with KRAS/NRAS and BRAF WT mCRC who were previously treated with chemotherapy (including oxaliplatin, irinotecan and 5-fluorouracil, anti-VEGF agents) and with anti-EGFR mAb therapy for ≥ 16 weeks.

The study will comprise two parts a Safety Lead-In part in approximately 25 participants and a Randomised part in approximately 500 participants.

The study design is depicted in [Figure \(4.1.1\) 1](#).

Figure (4.1.1) 1 - CL3-95026-001 Study Design

AE = adverse event; DLT = dose-limiting toxicity; ECD = extracellular domain; EGFR = epidermal growth factor receptor; mCRC = metastatic colorectal cancer; TEAE = treatment-emergent adverse event; STEAE = serious treatment emergent adverse events

Figure (4.1.1) 2 - Study plan for the Safety Lead-In Part

[figure not shown]
[figure not shown]

Figure (4.1.1) 3 - Study plan for the Randomised part

The study start is defined as the date of the first visit of the first participant.

The study will be divided into the following periods for each participant:

- Screening visit/Screening period (maximum 28 days):
 - Screening visit: after signature of the Informed Consent Form(s) (ICF) to check screening criteria and decide if participant can be screened for the study.
 - Screening period: if the participant is screened in the study, check the inclusion and exclusion criteria and decide if participant can be included in the study.
 - Randomisation: included participants will be randomly assigned to one of the two treatment groups:
 - Arm A: trifluridine/tipiracil + futuximab/modotuximab.
 - Arm B: trifluridine/tipiracil.
- Treatment period: participants will be treated until they meet a discontinuation criterion as described in [Section 5.8.1](#). The participants should receive the first dose of first IMP (Day 1 of Cycle 1) within 3 days after inclusion (in the Safety Lead-in part) or after randomisation.
- Withdrawal visit (WV): should be conducted within approximately 4 weeks following the date of study treatment withdrawal and before the start of a new anticancer therapy.
- Follow-up period: after the WV the participant will be followed every 8 weeks (\pm 10 calendar days):

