5.8. Participant withdrawal

5.8.1. Withdrawal criteria

A participant may be withdrawn from the study at any time for any reason (*e.g.* lost to follow-up, withdrawal of consent, AE). Premature discontinuation of IMP does not mean that the participant prematurely stops the participation in the study.

Information to be collected during the last visit of these participants is given in [Section 5.8.2](#). These follow-up modalities are used to ensure the efficacy and safety evaluation of all participants who received IMP.

The reasons for **premature IMP discontinuation** are:

- **Adverse events**, incompatible with continuation of the IMP according to the judgment of the investigator, including no recovery in safety parameters.
- **Pregnancy** (for reporting, see [Section 8.9.2.3](#)).
- **Major protocol deviation** if it interferes with the study evaluations and/or if it jeopardises participant's safety, *e.g.* any medical event requiring administration of an unauthorised concomitant treatment ([Section 6.3](#)).
- **Radiologic progressive disease** documented by CT-scan or MRI.
- **Clinical progressive disease** manifested by symptomatic deterioration.
- **Non-medical reason** (*e.g.* consent withdrawal, participant's removal).
- **Other, physician decision** (for reasons that cannot be included in any of the criteria listed above for example: availability of a better therapeutic alternative for the participant).

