5.8.2. Procedure

Upon discontinuation of study treatment, the investigator must:

- Notify the sponsor immediately.
- Register the end of treatment for the patient in the IWRS for Randomised part.

- Record this information in the e-CRF, specifying the reason for the study participant's withdrawal. If there are several reasons, the investigator must indicate the main reason. The investigator should document the discontinuation in the corresponding medical file.

A withdrawal visit should always be suggested to the participant and should take place within 4 weeks after the last IMP administration and prior to the start of a new anticancer therapy.

In the case of discontinuation due to an AE (event requiring immediate notification [ERIN] or not), the investigator must make every effort to collect the information relating to the outcome of the event. If necessary, the information will be collected afterwards ([Section 8.9.2.1](#)). This information is recorded in that part of the e-CRF form which concerns AEs. If the investigator cannot collect the information from a visit, he must collect it from the doctor ensuring the follow-up of the participant.

In case of discontinuation due to an ERIN, please refer to [Section 8.7](#).

Follow-up period:

After the withdrawal visit, a follow-up will be done every 8 weeks (\pm 10 calendar days):

- For tumour assessment (unless patient had discontinued IMPs for radiologic disease progression or withdrawal of consent) until radiologic progression regardless of initiation of a new anticancer therapy.
- For survival status until death or the end of the study (whichever occur first). This follow-up can be done remotely by using various telecommunication technologies including but not limited to phone, internet and shared electronic medical records.

Participants are at any time free to discontinue their participation in the study. If participants wish to withdraw their consent to treatment period (*i.e.* both IMPs and study assessments), they will be asked if they are willing to continue with Follow-up period for survival status (which can be done by phone). If participants wish to withdraw their consent to further participation in the study entirely (treatment period and follow-up period), this should be clearly documented in the patient notes and in the clinical study database. During the post-withdrawal follow-up period, the patient can participate to another clinical trial.

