7.2. Methods and measurement times

7.2.1. Measurement times

Tumour assessments/imaging of the chest, abdomen, and pelvis at a minimum (other localisations if clinically indicated) will be obtained at each time point listed below for all participants:

- **Baseline:** tumour assessment will be done within 28 days prior to the first administration of first IMP. Images obtained prior to participant signed ICF may be used if the date of the images is within 28 days of randomisation (first administration of first IMP for Safety Lead-In part) and if in line with methods and techniques that will be used during study.
- **Treatment period:** tumour assessments will be done every 8 weeks from C1D1 (\pm 7 calendar days) until radiologic progression is documented.
- **Withdrawal visit:** tumour assessments will be done only if not performed within previous 8 weeks. Every effort should be made to perform the WV tumour assessments prior to the start of new anti-cancer therapy.
- **Follow-up period:** tumour assessments will be done for participants who were withdrawn for reasons other than radiologic disease progression or consent withdrawal, every 8 weeks (\pm 10 calendar days) during the follow up period until the participant experienced radiologic progression, regardless of the initiation of a new anticancer therapy.

Note: If the investigator determines that a participant develops clinical progression manifested by symptomatic deterioration but not supported by radiologic evidence of progression, the participant should stop study treatments. Symptoms of clinical progression must be documented in the participant's source documents and in AE form (if judged by the investigator to be more severe than expected for the participant's condition). Tumour assessments will continue every 8 weeks (\pm 10 calendar days) until a radiologic progression is documented.

Note: Evaluation of secondary anti-tumour efficacy endpoints in the Randomised part (PFS, OR, DC, DoR, TTR) will be based on the investigator's assessment.

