10.1.1. Analysis sets / Treatment groups

10.1.1.1. Analysis sets

Full Analysis Set (FAS): In accordance with the ITT principle and [Section 5.2.1](#) of ICH E9 guideline,³⁹ all participants to whom a therapeutic unit was randomly assigned using IWRS. Participants in the FAS will be analysed in the arm they were assigned by randomisation. FAS will be used in all efficacy analyses of Randomised part, unless otherwise specified.

Safety Set (SS): All participants having taken at least one dose of IMPs. Participants will be analysed according to the treatment actually received. SS will be used in all analyses of Safety Lead-In part and safety analyses of Phase 3 part.

Per-Protocol Set (PPS): all participants in the FAS who do not violate the terms of the protocol in a way that would affect the study outcome significantly. Participants not fulfilling one of the following criteria will not be included in the PPS:

- Must have histologically or cytologically confirmed adenocarcinoma of mCRC [Screening criterion #2].
- Should be without RAS (KRAS and NRAS) mutations and without BRAF mutation [Screening criterion #3].
- Must have received at least 2 prior regimens of standard chemotherapy for mCRC and had demonstrated progressive disease or intolerance to their last regimen [Screening criterion #5].
- Should have received previous treatment with commercially available anti-EGFR mAbs for ≥ 16 weeks [Screening criterion #6].
- ECOG performance status 0 or 1 [Screening criterion #9].
- Currently receiving or having received anticancer therapies within 4 weeks prior to first IMP administration [Non-screening criterion #14].

PRO Analysis Set: All participants from the FAS who have completed screening and at least one post baseline assessment. Quality of life (QoL) endpoints will be evaluated on PRO Analysis Set.

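### The Synopsis and Section 5.8.1 tie follow-up to dosed participants, and no section gives someone randomised but never dosed a start date for survival contacts or scans

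*Protocol*

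**What the plan says.** **Who is followed.** The Synopsis (Follow-up period) states "After the withdrawal visit, all treated participants will be followed every 8 weeks", for tumour assessment and survival status. Section 5.8.1 says "These follow-up modalities are used to ensure the efficacy and safety evaluation of all participants who received IMP". Section 4.1.1 does not use the word treated: "Follow-up period: after the WV the participant will be followed every 8 weeks". Section 5.8.2 likewise describes follow-up after the withdrawal visit without limiting it to treated participants.

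**When follow-up starts.** In 4.1.1 the withdrawal visit is timed from treatment withdrawal. In 5.8.2 it "should take place within 4 weeks after the last IMP administration and prior to the start of a new anticancer therapy". Section 7.2.1 says imaging "will be obtained at each time point listed below for all participants", but the on-treatment entry is that "tumour assessments will be done every 8 weeks from C1D1". The follow-up entry leaves out participants who withdrew consent.

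**Who is analysed.** The FAS (10.1.1.1) is "all participants to whom a therapeutic unit was randomly assigned using IWRS", analysed as randomised. The primary OS estimand and one of the two PFS estimands follow a treatment policy strategy (Table (10.1.2.4.2) 1). OS and PFS both run from randomisation. Participants with no recorded death are censored for OS at the last date known alive or the cut-off, whichever is earlier (10.1.2.4.2.1).

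**The concern.** A treatment policy estimand in everyone randomised needs vital status, and for PFS tumour status, on everyone randomised. A follow-up rule written for dosed participants does not ask for that. The trial is open-label, so a control participant may decline on learning the allocation. That person has no C1D1, no last dose and no withdrawal visit from which to count.

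If such participants are more common in one arm, and their prognosis differs from that of the others, censoring them early moves the comparison away from all randomised participants towards those who were dosed. Data that were never collected cannot be recovered at the analysis stage.

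**Working it through.** **1. Anchors for a participant randomised but never dosed**

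| Item | Section | Counted from | Usable date? |
|---|---|---|---|
| Withdrawal visit | 4.1.1, 5.8.2 | Treatment withdrawal; last IMP | No |
| Survival contacts | Synopsis, 4.1.1, 5.8.2 | Withdrawal visit | No; 5.8.2 makes an offer on withdrawal of consent to treatment, with no start date |
| On-treatment scans | 7.2.1, Table (4.1.2) 2 | C1D1 | No |
| Follow-up scans | 5.8.2, 7.2.1 | Follow-up period | No; consent withdrawals excluded |
| ECOG, for TtPS2 | 8.2.2 | Cycle visits, withdrawal visit | No scheduled date after inclusion |
| Next therapy, for TTNT | 5.8.2, 6.3 | To be recorded; collected at follow-up visits | No scheduled contact |

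**2. The plan's own figure (10.2).** Inputs: 500 randomised 1:1, medians 8.5 and 12 months (HR 8.5/12 = 0.708, stated as 0.71), one-sided 0.025, 383 events, 90% power, analysis at 37.5 months.
- A fixed design by Schoenfeld's formula needs 359 events at HR 0.71.
- With the Table (10.2) 1 boundaries at 128, 255 and 383 events, simulated power is 0.901 at HR 0.708 and 0.897 at 0.71. Type I error is 0.0250 ignoring the non-binding futility bounds.
- Timing: exponential survival, accrual rising linearly to 30 per month over 21 months, and the 7% loss read as per year (hazard -ln(0.93)/12 = 0.00605 per month; the plan gives no time unit). The model reaches 383 events at 37.7 months.

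The stated design reproduces.

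**3. How many might never be dosed.** Section 2.2.2 describes the open-label Phase 2 study Sym004-05. Its control arm is given as "Arm C; 85 patients, 78 treated", so 85 - 78 = 7 untreated (7/85 = 8.2%). On 9/6 mg/kg, 86 - 84 = 2 (2/86 = 2.3%); on 12 mg/kg, 0 of 83. Seven of the nine were controls. Assumption: the control and 9/6 rates apply here.
- Control: 250 × 7/85 = 20.6
- Experimental: 250 × 2/86 = 5.8
- Total: 26.4 of 500 = 5.3%

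**4. Events, if none of them is followed** (model of step 2; the never-dosed given their own arm's hazard)
- Events at 37.5 months: 382.1 with all followed, 361.2 without; difference 20.9.
- Time to 383 events: 37.7 months with all followed, 42.4 without.
- With no other loss to follow-up: 34.7 and 37.8 months.

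**5. Hazard ratio, if none of them is followed.** Large-sample Cox simulation, 400,000 per arm, 20 months of follow-up. Assumption: the never-dosed in both arms have k times the control hazard (k = 0.5 is a median of 8.5/0.5 = 17 months; k = 2 is 8.5/2 = 4.25 months).

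| HR among treated | k | All randomised | Never-dosed censored at day 0 | Difference |
|---|---|---|---|---|
| 0.708 | 0.5 | 0.743 | 0.707 | -0.036 |
| 0.708 | 1 | 0.715 | 0.708 | -0.007 |
| 0.708 | 2 | 0.688 | 0.707 | +0.019 |
| 1.00 | 0.5 | 1.037 | 0.995 | -0.042 |
| 1.00 | 1 | 0.997 | 0.997 | 0.000 |
| 1.00 | 2 | 0.960 | 0.995 | +0.035 |

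**The case against.** A reader might infer that never-dosed participants get no OS follow-up at all and are all censored near day 1. The documents do not support that.
- The treated limit is Synopsis wording. The 5.8.1 sentence states a purpose, and the same section says that stopping IMP does not end participation.
- Section 5.8.2 has sites ask anyone withdrawing consent to the treatment period whether survival follow-up may continue, by phone if wanted. No prior dose is required. This is the likely route for a control who declines after allocation.
- Section 5.8.2 ends follow-up only at death or at the end or termination of the study.
- Subsequent anticancer therapy is to be recorded, so TTNT is not simply lost.

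This stands for OS, and it makes steps 4 and 5 an upper bound. It does not close the gap. The offer has no start date, covers survival status only, and does not reach someone left undosed for another reason. Section 8.9.1 requires deaths before the first dose to be reported but schedules no contact, so a death a site hears of would count while survivors are censored early.

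For scans, footnote 6d of Table (4.1.2) 2 counts from the previous assessment, which could be read as the baseline scan. But it applies within a follow-up period that opens after the withdrawal visit, and it excludes consent withdrawals.

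Three further inferences should be resisted:
- **That 8.2% against 2.3% forecasts this trial.** The Phase 2 control was capecitabine, 5-FU or best supportive care, and Fisher's exact p for control against 9/6 is 0.10.
- **That power falls.** The analysis is event-driven, so power at 383 events is unchanged; the cost is time.
- **That every scan needs re-clocking.** Randomisation is at most 3 days before C1D1 and the scan window is ±7 days, so for dosed participants little would change.

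**Conclusion.** The point holds as a conflict between a stated follow-up rule and the estimands it must serve, together with a missing schedule. The Synopsis and 5.8.1 describe follow-up of dosed participants. The body text does not repeat the limit but starts every post-baseline contact from a treatment date. The OS gap is partial because of the telephone offer in 5.8.2. The PFS gap is fuller, because someone never dosed has no scan date independent of treatment and is left out of follow-up scans if consent was withdrawn.

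The size is illustrative and an upper bound: about 21 controls and 6 experimental participants, about 21 fewer OS events at 37.5 months, a delay from about 38 to 42 months, and an HR error of up to about 0.03 to 0.04. The sign is unknown because it depends on the prognosis of the never-dosed, which the documents do not give. These figures rest on the Sym004-05 rates applying under a different control, on no follow-up of any of these participants, on exponential survival, and on reading the 7% loss as annual.

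The SAP (Introduction) records that the Randomised part was cancelled, so no comparison was affected. The point concerns the plan as written and any reuse of the design.

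**What to change.** For the Randomised part, reword the Synopsis so that follow-up covers all randomised participants, whether or not treated, unless consent to follow-up is withdrawn. Align 4.1.1, 5.8.1, 5.8.2, 7.2.1 and Table (4.1.2) 2 with it. For participants never dosed, start the 8-weekly survival contact, the collection of next anticancer therapy and, where they agree, tumour assessments from the randomisation date. Leave the scan clock for dosed participants as it is.

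The cost is wording plus remote contacts, which 4.1.1 and 5.8.2 already allow, for an estimated 15 to 30 participants. Some of them will decline scans, so the PFS gap would narrow rather than close.
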